9.0 TRIAL PLAN

9.1 Trial Procedures

The following sections describe the trial procedures and data to be collected. For each procedure, subjects are to be assessed by the same investigator or site personnel whenever possible. The schedule of procedures is shown in Section 2.1. All procedures must be performed by qualified and trained staff. All information collected should be recorded in the appropriate source documentation and in the subject's eCRFs.

9.1.1 Informed Consent

The requirements of the ICF are described in Section 15.2.

Informed consent must be obtained before any protocol-directed procedures are performed.

A unique subject number will be assigned to each subject by the IRT after informed consent is obtained. If all eligibility criteria are fulfilled (Sections 7.1 and 7.2), this subject number will be used throughout the trial. Subject numbers assigned to subjects who fail screening should not be reused (Section 9.1.9).

9.1.2 Demographics, Medical History and Prior Medications

Demographic information to be obtained will include age/date of birth (if applicable), sex, race (and ethnicity) as described by the subject's LAR.

Medical history will also be collected, including any medical history that may be relevant to subject eligibility for trial participation such as prior vaccinations, concomitant medications, and previous and ongoing illnesses and/or injuries. Relevant medical history can also include any medical history that contributes to the understanding of an AE that occurs during trial participation if it represents an exacerbation of an underlying disease/preexisting problem. Medical history (including corresponding medication) to be obtained will include any significant conditions or diseases that have resolved at or prior to signing the ICF. The subject's LAR will also be asked whether the child is breastfeeding.

Adverse medical occurrences emerging during the time between signing the ICF and the first administration of the trial vaccine will be recorded in the medical history eCRF page. If such an adverse medical occurrence is assessed as related to a screening procedure this should be recorded as an AE related to trial procedure in the eCRF.

Details of all medications, vaccines and blood products administered to the subjects in the following timeframes will be collected as *prior* (prior to Visit 1 [age 2 months]), or *concomitant* (from Visit 1 [age 2 months] to Visit 5 [age 12 months]).

Antipyretics and/or analgesic medications within 24 hours prior to trial vaccine administration (at Visit 2) and the reason for their use (prophylaxis versus treatment) must be documented. Administration of the trial vaccine should be delayed if the subject has received antipyretics within 24 hours prior to trial vaccine administration.

Medications taken for prophylaxis are those intended to prevent the onset of AEs following vaccination. Medications taken for treatment are intended to reduce or eliminate the presence of symptoms that are present.

These data must be recorded in the source documents.

9.1.3 Documentation of Trial Entry/Randomization

Only subjects for whom there is a signed ICF, and who meet all of the inclusion criteria (Section 7.1) and none of the exclusion criteria (Section 7.2), will be eligible for entry into the trial (Visit 1) and randomization/entry into the active phase (Visit 2). The randomization schedule will be created and controlled by the IRT provider. The randomization specification will be approved by the sponsor's trial statistician, or designee.

If the subject is ineligible for randomization or terminated before Visit 2, the investigator should record the primary reason for failure on the subject screening and enrollment log. These subjects will be replaced.

9.1.4 Physical Examination

Physical examinations must be performed by a qualified health professional in accordance with local regulations and as listed within the site responsibility delegation log. For this trial, a physical examination includes the assessment of general appearance, assessment of extremities (including skin over the intended injection site), heart rate and temperature. Weight, length and head circumference will be recorded. A complete physical exam will be performed at trial entry (age 2 months) prior to routine childhood vaccine administration, and again at Visit 2 (age 4 months), prior to trial vaccine administration, according to the investigator's standard practice. Additional physical examinations may be performed if indicated by review of the subject's medical history. The findings should be documented in the subject's source document.

A symptom-directed physical examination may be performed if deemed necessary.

9.1.5 Vital Signs

Vital signs measured will include heart rate and body temperature.

9.1.6 Immunogenicity Assessments

Subjects in both trial arms will undergo blood sampling for serological immunogenicity testing at two clinic visits:

- Visit 2 (age 4 months; pre-trial vaccine dose 1).

CONFIDENTIAL

- Visit 4 (age ~7 months; 28 days post-trial vaccine dose 2).

All samples must be collected in accordance with acceptable laboratory procedures. The maximum volume of blood taken at Visit 2 is 4 mL and at Visit 4 is 6 mL, and the total volume of blood for the trial is maximum 10 mL.

9.1.7 Processing, Labeling and Storage of Biological Samples

All biological samples (e.g., blood and serum) will be processed, labeled and stored according to the laboratory manual or other appropriate guideline provided to the site.

9.1.8 Safety Assessments

Safety assessments will begin at Visit 1 for MAAEs, SAEs, and AEs leading to withdrawal from the trial.

Safety assessments by site staff are planned immediately following each dose of trial vaccine. In addition, the subject's LAR will collect solicited local and systemic reactions daily for the 7 days (including day of administration) post-dose 1 (when the subject is aged 4 months) and dose 2 (when the subject is aged 6 months) of the trial vaccine via eDiary.

Safety assessments will also be made when the subject returns to the clinic for the second dose of trial vaccine (Visit 3), when the subject is aged 6 months, then at Visit 4 and Visit 5 (whether subject is aged ~7 months and 12 months, respectively). These assessments will include collection and recording of unsolicited AEs (serious and non-serious), withdrawal from trial vaccine (Visit 2 and Visit 3), withdrawal from trial, SAEs and MAAEs.

Refer to Section 10.1 for safety definitions. Details on collection and reporting of AEs are in Section 10.5.

9.1.9 Documentation of Subjects Who Are Not Randomized

Investigators must account for all subjects for who there is a signed ICF. If the subject is found to be not eligible at this visit, the investigator should complete the eCRF.

The primary reason for non-randomization is recorded in the eCRF using the following categories:

- Screen failure (did not meet one or more inclusion criteria or did meet one or more exclusion criteria).
- Withdrawal by the subject's LAR.
- Withdrawal by the investigator.
- Trial terminated by the sponsor.

Subject numbers assigned to subjects who fail screening should not be re-used.

9.2 Monitoring Subject Compliance

The investigator will record all injections of routine childhood vaccines and trial vaccines given to the subject.

9.3 Schedule of Observations and Procedures

The schedule for all trial-related procedures for all evaluations is shown in Section 2.2. Assessments should be completed at the designated visit(s)/time point(s).

The subject's approximate age at each visit is:

- **Visit 1:** 2 months.
- **Visit 2:** 4 months.
- **Visit 3:** 6 months.
- **Visit 4:** ~7 months.
- **Visit 5:** 12 months.

9.3.1 Pre-Vaccination Procedures (Visits 1, 2 and 3)

1. Informed consent or ICF (Section 9.1.1; Visit 1 only).
2. Assessment of eligibility criteria (Section 7.1 and Section 7.2).
3. Assessment of criteria for delay of vaccination (Section 7.3).
4. Demographics (Section 9.1.2; Visit 1 only).
5. Medical history (Section 9.1.2; Visit 1 and Visit 2).
6. Medication/vaccination history (Section 9.1.2).
7. Randomization (Section 8.6; Visit 2).
8. Documentation of trial entrance (Section 9.1.3; Visit 1 only).
9. Complete physical examination (Section 9.1.4).
10. Vital signs (Section 9.1.5).
11. Blood sampling (~4 mL) (Section 9.1.6; Visit 2).
12. Concomitant medications (Section 9.1.2).

9.3.2 Vaccination Procedures (Visits 1, 2 and 3)

After completing all pre-vaccination procedures (Section 9.3.1), randomizing the subject at Visit 2, and assessing the criteria for the delay of routine childhood vaccine (Visits 1, 2 and 3) and trial vaccine administration (Visits 2 and 3), the investigator will administer the vaccines

CONFIDENTIAL

according to the procedures described in Section 8.5. At Visit 2, the investigator will confirm that the subject does not meet any criteria for delaying, or premature discontinuation of, additional routine childhood vaccine or trial vaccine administration, as described in Section 7.3.

9.3.3 Post Vaccination Procedures (Visits 1, 2 and 3)

After routine pediatric vaccine administration (Visit 1), the subject will be observed for at least 30 minutes including observation for AEs and body temperature measurement. Information should be recorded in the eCRF.

After trial vaccine administration (Visit 2 and Visit 3), the subject will be observed for at least 30 minutes including observation for unsolicited AEs, solicited local and systemic reactions and body temperature measurement. Information should be recorded in the eCRF.

The following post-vaccination procedures will be performed at Visit 2:

- The individual(s) who will enter the information into the eDiary will be trained on how to measure solicited local reactions and body temperature, how to complete the electronic diary card (eDiary) and how often to complete the eDiary. Training should be directed at the individual(s) who will perform the measurements of solicited local reactions (specifying that the RIGHT thigh must be evaluated) and those who will enter the information into the eDiary. This individual may or may not be the subject's LAR, but if a person other than the subject's LAR enters information into the eDiary, this person's identity must be documented in the source documents and this person must receive training on the eDiary. Training of the subject's LAR or these individuals on how to measure an injection site reaction, and how to take body temperature, and how to record the information in the eDiary, should be performed while the subject is under observation after trial vaccine administration.

eDiary instructions must include the following:

- The individual(s) who will enter the information into the eDiary must understand that timely completion of the eDiary on a daily basis is a critical component of trial participation.

Please note:

The eDiary will be the only source document allowed for remote collection of solicited local and systemic reactions and body temperature measurements. The following additional rules apply to the documentation of safety information collected by eDiary:

- The eDiary should be reviewed with the subject's LAR.
- No corrections or additions to the eDiary will be allowed after it is reviewed with the investigator/designee.
- Any data that are identified as implausible or incorrect and confirmed by the subject's LAR to be an error, should be corrected by the investigator/designee within the allowed review time.

CONFIDENTIAL

- Starting on the day of trial vaccine administration, the subject's LAR will check for specific types of events at the injection site on the RIGHT thigh, any specific generalized symptoms (solicited systemic reactions), body temperature (rectal or axillary), any other symptoms or change in the subject's health status, and any medications given to the subject (excluding vitamins and minerals). These solicited reactions and body temperature will be recorded in the eDiary. Other symptoms and medications will be recorded in the memory aid section of the eDiary. Measurements should preferably take place in the evening.
- Temperature measurement is to be performed daily using the thermometer provided by the site. If the subject feels unusually hot or cold during the day, the subject's LAR should check their temperature. If the subject has a fever, the highest body temperature observed that day should be recorded on the eDiary.
- The subject's LAR should use the ruler provided by the site to measure the solicited local reactions.
- The collection on the eDiary of body temperature, solicited local and systemic reactions will continue for a total of 7 days (including day of administration) after each trial vaccine administration (Visits 2 and 3). The recording of other symptoms and concomitant medications in the memory aid section of the eDiary will continue for 28 days (including day of administration) after trial vaccine administration.

The site staff should schedule the next trial activity reminder call/message or visit.

The site staff will provide a written reminder of the next planned trial activity to the subject's LAR. The site staff will remind the subject's LAR to complete the eDiary daily (up to Day 7 after each trial vaccine administration), and record other symptoms and concomitant medications in the memory aid section of the eDiary as needed (up to Day 28 after each trial vaccine administration), to contact the site if there are any questions and to contact the site immediately (or as soon as the subject is medically stable) if the subject has a medical condition that leads to a hospitalization or an emergency room visit. All contact details will be provided to the subject's LAR.

9.3.4 Phone Contacts (Call 1 and Call 2)

Post-vaccination phone calls will be performed 7 days post each dose of trial vaccine (Call 1 at 7 days after Visit 2, and Call 2 at 7 days after Visit 3). The purpose is to review the completed eDiary with the subject's LAR. If the subject's LAR wishes to describe safety information, this information should only be collected by a trained healthcare professional at the site, and the safety data described must be recorded in source documents. The subject's LAR should be reminded to continue recording the information about other symptoms and concomitant medications in the memory aid section of the eDiary and to contact the site via the telephone number provided in the ICF to discuss medical questions.

9.3.5 Site Visits After Vaccination (Visit 4)

A site visit that does not include a trial vaccine administration will occur when the subject is approximately 7 months old (Visit 4). Procedures include targeted physical examination, vital signs, eDiary memory aid review and blood draw (Visit 4 only). The healthcare professional reviewing these data will discuss the AEs (if any) reported by the subject's LAR and will determine if any additional diagnoses and/or AEs are present and/or if concomitant medications have been used. Blood (~ 6 mL) should be taken at Visit 4 from the subject using an aseptic venipuncture technique for serological immunogenicity testing. At Visit 4, the site should schedule the next site visit with the subject's LAR. The subject's LAR will receive a written reminder of the next planned trial activity. The subject's LAR will be reminded to contact the site if there are any questions and to contact the site immediately (or as soon as the subject is medically stable) if the subject has a medical condition that leads to a hospitalization or an emergency room visit.

9.3.6 Final (End of Trial) Visit

The final (end of trial) visit will be performed at Visit 5 when the subject has reached the age of 12 months. The subject will undergo a physical examination at this visit and the applicable safety assessments (Section 9.1.8). If a subject terminates earlier, the final (end of trial) visit procedures should be performed at their last trial visit, if possible. The investigator must complete the end of trial eCRF page for all subjects who received trial vaccine.

9.3.7 Post-Trial Care

No post-trial care will be provided.

9.4 Biological Sample Retention and Destruction

In this trial, specimens for immune response testing will be collected as described in Section 9.1.6. After blood draw and serum processing, the serum samples will be preserved and retained at a central laboratory that was contracted by the sponsor for this purpose for up to but not longer than 20 years or as required by applicable law. The sponsor has put into place a system to protect the subjects' personal information to ensure optimal confidentiality and defined standard processes for sample and data collection, storage, analysis, and destruction.

Serum samples will be used for the analyses defined in this protocol, but can also, with permission from the subject's LAR, be used to assess, improve or develop tests related to norovirus or HIL-214 that will allow more reliable measurement of the response to HIL-214.

If the subject's LAR does not consent to future testing of samples on the ICF, the subject can still participate in the trial.

10.0 ADVERSE EVENTS

10.1 Definitions

10.1.1 Adverse Events

An AE is defined as any untoward medical occurrence in a clinical investigation subject administered a trial vaccine; it does not necessarily have to have a causal relationship with trial vaccine administration. An AE is also defined as any untoward medical occurrence in a clinical investigation subject from the time they enter the trial.

An AE can therefore be any unfavorable and unintended sign (e.g., a clinically significant abnormal laboratory finding), symptom, or disease temporally associated with the administration of an trial vaccine whether or not it is considered related to the trial vaccine.

AEs will be graded by the investigator in the following manner:

Mild	Grade 1	
• Awareness of symptoms that are easily tolerated, causing minimal discomfort and not interfering with everyday activities. Relieved with or without symptomatic treatment.
Moderate	Grade 2	
• Sufficient discomfort is present to cause interference with normal activity. Only partially relieved with symptomatic treatment.
Severe	Grade 3	
• Extreme distress, causing significant impairment of functioning or incapacitation. Prevents normal everyday activities. Not relieved with symptomatic treatment.

10.1.2 Solicited Adverse Events

The occurrence of selected indicators of safety will be measured/collected for 7 days (including day of administration) following administration of each trial vaccine dose (including the day of administration) and will be recorded on the local and systemic AE CRF page as applicable and as listed in Table 10.1.

Any solicited local (in the RIGHT thigh) or systemic reactions observed as continuing beyond 7 days (including day of administration) following each trial vaccine dose will be recorded as an AE on the AE CRF for follow-up. For these persistent/prolonged solicited reactions the end date will be captured on the AE CRF to permit a separate analysis from the unsolicited AEs (see Section 10.4.2).

Table 10.1 Solicited Local (Injection Site) and Systemic Reactions

Solicited local (injection site) reactions:	Pain Erythema Induration Swelling
Systemic adverse events:	Drowsiness Irritability/fussiness Loss of appetite Fever* Vomiting Diarrhea

Body temperature will be collected and recorded. *Fever is defined as body temperature greater than or equal to 38°C (100.4°F) regardless of method used [16].

The severity of solicited safety parameters will be assessed as described in Table 10.2.

Table 10.2 Solicited Safety Parameters

Adverse Event	Severity Grade	Intensity
Pain at injection site	0	None
	1	Mild: Minor reaction to touch
	2	Moderate: Cries/protests on touch
	3	Severe: Cries when limb is moved/spontaneously painful
Erythema at injection site ^(a)	0	≤ 10 mm
	1	Mild: $>10 - \leq 20$ mm
	2	Moderate: $>20 - \leq 40$ mm
	3	Severe: >40 mm
Induration at injection site ^(a)	0	≤ 10 mm
	1	Mild: $>10 - \leq 20$ mm
	2	Moderate: $>20 - \leq 40$ mm
	3	Severe: >40 mm
Swelling at injection site ^(a)	0	≤ 10 mm
	1	Mild: $>10 - \leq 20$ mm
	2	Moderate: $>20 - \leq 40$ mm
	3	Severe: >40 mm
Drowsiness	0	Behavior as usual
	1	Mild: Drowsiness easily tolerated
	2	Moderate: Drowsiness that interferes with normal activity
	3	Severe: Drowsiness that prevents normal activity
Irritability/fussiness	0	Behavior as usual
	1	Mild: Crying more than usual/no effect on normal activity
	2	Moderate: Crying more than usual/interferes with normal activity
	3	Severe: Crying that cannot be comforted/prevents normal activity
Loss of appetite	0	Appetite as usual
	1	Mild: Eating less than usual/no effect on normal activity
	2	Moderate: Eating less than usual/interferes with normal activity
	3	Severe: Not eating at all
Vomiting	0	None
	1	Mild: No interference with activity or 1 – 2 episodes/24h
	2	Moderate: Some interference with activity or >2 episodes/24h
	3	Severe: Prevents activity, requires outpatient IV hydration
Diarrhea	0	None
	1	Mild: 2 – 3 loose stools/24h
	2	Moderate: 4 – 5 loose stools/24h
	3	Severe: ≥ 6 watery stools/24h or requires outpatient IV hydration
Fever ^(b)	Record body temperature in °C/°F	

Abbreviations: h, hour; IV, intravenous.

(a) The greatest surface diameter will be recorded in mm on the diary.

(b) Fever is defined as body temperature greater than or equal to 38°C (100.4°F) regardless of method used [16].

10.1.3 Adverse Events of Special Interest

Not applicable. No adverse event of special interest (AESI) has been identified for this trial.

CONFIDENTIAL

10.1.4 Medically-attended Adverse Events

MAAEs are defined as AEs leading to an unscheduled visit to or by a healthcare professional including visits to an emergency department, but not fulfilling seriousness criteria.

10.1.5 Serious Adverse Events

An SAE is defined as any untoward medical occurrence that:

1. Results in DEATH.
2. Is LIFE THREATENING.
 - The term life threatening refers to an event in which the subject was at risk of death at the time of the event; it does not refer to an event that hypothetically might have caused death if it were more severe.
3. Requires inpatient HOSPITALIZATION or prolongation of existing hospitalization.
4. Results in persistent or significant DISABILITY/INCAPACITY.
5. Leads to a CONGENITAL ANOMALY/BIRTH DEFECT in the offspring of a subject (not applicable).
6. Is an IMPORTANT MEDICAL EVENT that satisfies any of the following:
 - May require intervention to prevent items 1 to 5 above.
 - May expose the subject to danger, even though the event is not immediately life threatening or fatal or does not result in hospitalization.

10.2 Causality of Adverse Events

Relationship (causality) to the trial vaccine will also be assessed by the investigator. The relationship of each unsolicited AE to the trial vaccine and routine vaccine will be assessed using the following categories:

Related: There is suspicion that there is a relationship between the trial vaccine and the AE (without determining the extent of probability); there is a reasonable possibility that the trial vaccine contributed to the AE.

Not Related: There is no suspicion that there is a relationship between the trial vaccine and the AE; there are other more likely causes and administration of the trial vaccine is not suspected to have contributed to the AE.

Solicited local and systemic reactions are deemed related to trial vaccine by default.

10.2.1 Relationship to Trial Procedures

Relationship (causality) to trial procedures should be determined for all AEs.

The relationship should be assessed as related to trial procedure if the investigator considers that there is a reasonable possibility that an event is due to a trial procedure. Otherwise, the relationship should be assessed as not related.

AEs deemed related to routine pediatric vaccines administered as part of the trial will be recorded as related to trial procedure.

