10.4 Procedures

10.4.1 Collection and Reporting Procedures

All AEs, whether considered related to the use of the trial vaccine or not, must be monitored by the investigator until symptoms subside and any abnormal laboratory values have returned to baseline, or until there is a satisfactory explanation for the changes observed, or until death, in which case a full autopsy report should be supplied, if possible. All findings must be reported on the AE eCRF and on the SAE form*, if necessary (see Section 10.4.4). All findings in subjects experiencing AEs must also be documented in that subject's source documents. Any unsolicited

AE will be recorded by the subject's LAR for 28 days after Dose 1 (including day of administration; administered when the subject is aged 4 months) and for 28 days after Dose 2 (including day of administration; administered when the subject is aged 6 months) via the eDiary as a memory aid for reporting to the site at the subsequent clinic visit. AEs leading to trial vaccine discontinuation will be collected up to the second trial vaccine dose administration and AEs leading to withdrawal from the trial will be collected throughout the trial. Even if the subject is deemed ineligible to receive further doses of trial vaccine and/or routine vaccine(s), all efforts should be made to continue the collection of safety data according to the protocol. Attempts should also be made to collect remaining blood samples, if the subject's LAR agrees.

The following information will be documented for each event:

- Reported term for the AE.
- Start and end date, duration.
- Serious (Y/N).
- Intensity.
- Investigator's opinion of the causality (relationship) between the event and administration of trial vaccine (related or not related).
- Investigator's opinion of the causality (relationship) to trial procedure(s), including the details of the suspected procedure.
- Action taken with the trial vaccine and/or routine vaccine(s).
- Outcome of event.

**SAE reporting will be done with an SAE form sent to [REDACTED] Back up encrypted email [REDACTED]*

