13.1.3 Safety Analysis

All safety summaries will be provided for each trial arm and overall.

Solicited reactions:

Solicited reactions will be assessed 30 minutes after administration of each dose of trial vaccine, and then daily for 7 days (including the day of administration). For each solicited reaction, the number and percentage of subjects who experienced an event will be computed, for each day from Day 1 to Day 7 post-dose (including the day of dose) and overall.

Solicited reactions will be summarized by severity. For subjects with more than 1 episode of the same event within an interval, the maximum severity will be used for tabulations.

Body temperature measurements will be summarized in categories (including fever, defined as temperature $\geq 38^{\circ}\text{C}$), without adjustment for the route of measurement. Summaries of the day of first onset of each event and the number of days subjects experienced each event will also be provided.

Data from the 30 minutes assessment of solicited reactions immediately post-vaccination will be summarized separately.

Unsolicited AEs:

Any unsolicited AEs, SAEs, MAAEs, and AEs leading to trial vaccine, routine vaccine or trial withdrawal, will be coded using MedDRA, and summarized by system organ class (SOC) and preferred term (PT) using number and percentage of subjects with an AE. Subjects with more than one occurrence for the term will be counted only once for this term. Unsolicited AEs will be collected up to 28 days after administration of each dose of trial vaccine and routine vaccine (including the day of administration); summaries will also be provided by event severity (mild, moderate, severe) and relationship (not related, related) to trial vaccine, routine vaccine or trial procedures. For subjects with more than one AE within an SOC or a PT, the AE with the maximum severity or strongest relationship within each SOC and each PT will be included in the summaries by severity or relationship, respectively.

Any unsolicited AEs will be summarized in the following 3 time intervals: 1) overall up to 28 days after each dose (including the day of administration), 2) with onset between 1 and 7 days after each dose (including the day of administration), and 3) with onset between 8 and 28 days after dose (including the day of administration).

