10.2.4.1 Summaries

The summaries for unsolicited AEs will be:

- Overall Overview of the occurrence of all AEs.
- The number and percentage of subjects with any unsolicited AE during the first 28 days (including day of administration) after each dose of trial vaccine overall.
- The number and percentage of subjects with any unsolicited AE during the first 28 days (including day of administration) after each dose of trial vaccine by severity.
- The number and percentage of subjects with any unsolicited AE during the first 28 days (including day of administration) after each dose of trial vaccine by relationship to trial vaccine.
- The number and percentage of subjects with any unsolicited AE during the first 28 days (including day of administration) after each dose of trial vaccine by relationship to trial procedure.

Listings will be presented for all unsolicited AEs.

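### The promised summary of AEs by relationship to routine vaccine has no dedicated data item or SAP table, and such events are reported under a trial-procedure label

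*Protocol*

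**What the plan says.** Three places treat routine vaccine as a causality target of its own:

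- Protocol 10.2: "The relationship of each unsolicited AE to the trial vaccine and routine vaccine will be assessed using the following categories".
- Protocol 13.1.3 plans summaries by "relationship (not related, related) to trial vaccine, routine vaccine or trial procedures".
- SAP 10.2.2 covers relationship to both trial and routine vaccinations, with related and not related as the two categories.

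Other places do not carry that through:

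- Protocol 10.2.1: "AEs deemed related to routine pediatric vaccines administered as part of the trial will be recorded as related to trial procedure".
- Protocol 10.4.1 lists two causality items per event. One is "causality (relationship) between the event and administration of trial vaccine (related or not related"); the other is "causality (relationship) to trial procedure(s), including the details of the suspected procedure".
- SAP 10.2.4.1 (unsolicited AEs) has one table by relationship to trial vaccine and one "after each dose of trial vaccine by relationship to trial procedure". SAP 10.2.5.1 (SAEs) and 10.2.6.1 (MAAEs) follow the same pattern. SAP 10.2.7.1 (AEs leading to withdrawal) has relationship to trial vaccination only.

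SAP section 13 records two changes from the protocol, the hepatitis B assay and the intercurrent-event strategy. Neither concerns relatedness.

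**The concern.** Occurrence by relatedness is part of the safety endpoints in Protocol 5.2.3 and SAP 4.2.3, and the trial is about giving HIL-214 together with other vaccines. A reader of the report would expect to see which events investigators attributed to the co-administered vaccines. Under the plan as written, those events appear in tables headed trial procedure, and no output shows them separately.

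Unsolicited reporting matters more than usual for the routine vaccines. Protocol 6.2 limits solicited reactions to the trial vaccine, and local ones are checked on the right thigh only (Protocol 9.3.3). The routine injections go into the left thigh (Protocol 8.4), so a local reaction there can enter the data only as an unsolicited AE. If it is judged related to a routine vaccine, 10.2.1 then places it under trial procedure.

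**Working it through.** There is no plan figure to reproduce. The check sets the sections side by side and works through the timing.

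**1. Relatedness targets by section**

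| Place | Trial vaccine | Routine vaccine | Trial procedure | Targets |
|---|---|---|---|---|
| Protocol 13.1.3 (planned summaries) | yes | yes | yes | 3 |
| Protocol 10.4.1 (items per event) | yes | no | yes | 2 |
| SAP 10.2.4.1 (unsolicited AEs) | yes | no | yes | 2 |
| SAP 10.2.5.1 (SAEs) | yes | no | yes | 2 |
| SAP 10.2.6.1 (MAAEs) | yes | no | yes | 2 |
| SAP 10.2.7.1 (withdrawal AEs) | yes | no | no | 1 |

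Routine vaccine is missing from the item list and from all four SAP lists. The 10.4.1 list does name routine vaccines for the action taken, but not for causality.

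**2. Definitions.** Protocol 10.2 asks for both assessments but words its categories for one product. Related means that "there is a reasonable possibility that the trial vaccine contributed to the AE", and Not Related is phrased the same way. The routine-vaccine assessment has no definition of its own.

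**3. What can fall into the procedure tables**

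- Routine vaccines (Protocol 8.4): two injections at each of Visits 2 and 3, plus oral RV1 at Visit 2, so 2 × 2 + 1 = 5 routine administrations alongside the two trial doses.
- Blood draws (Protocol 9.1.6): two, at Visits 2 and 4.

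**4. Timing for the unsolicited AE table.** The collection period is 28 days including the day of dosing, so Day 1 to Day 28.

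- Visit 2 draw: taken before any vaccination (Protocol 2.2, footnote h). SAP 10.2.4 summarises only AEs after the first trial dose, so a draw-related event counts only if it is recorded after that dose.
- Visit 4 draw: due 28 days after Visit 3, window +7 days. With dosing on Day 1, that is Day 28 + 1 = 29 to Day 28 + 7 + 1 = 36, after the period has closed.

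Draw-related events therefore have little room in this table, and routine-vaccine events would plausibly make up most of it.

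**5. Timing for SAEs and MAAEs.** Protocol 6.1 follows both throughout the trial, so events after the Visit 4 draw fall inside the period and mixing is more possible. For MAAEs this depends on which section governs: 10.4.3 also says throughout the trial, but 5.1.3 ends collection 28 days after dose 2, which puts the Visit 4 draw at or beyond the edge.

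**The case against.** The strongest case against has four parts.

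- **The information may be recoverable.** A reader might infer that the routine-vaccine summary cannot be produced. The documents do not support that. Protocol 10.2 requires the assessment, and the procedure item in 10.4.1 asks which procedure was suspected. This stands: the gap is in the specified data item and output, not shown to be in the data.
- **10.2.1 may add rather than replace.** It speaks of AEs already judged related to a routine vaccine, so it could mean that such events are also flagged under procedure. That reading is possible and the eCRF is not available to settle it. It would not supply the missing SAP tables.
- **Attribution to HIL-214 is intact.** A reader might infer that routine-vaccine events blur the HIL-214 safety result. They do not. Relationship to trial vaccine has its own item and its own table in every list. Both arms follow the same routine schedule, randomization is stratified by country, and the blinded comparison of arms does not rely on causality opinions. This stands in full.
- **If the unsolicited table is mostly routine-vaccine events, little is lost.** This is partly right: for that table the fault is mainly the label. But a reader would not know that the label means routine vaccine, and the argument carries less weight for SAEs and MAAEs.

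Individual listings of unsolicited AEs, SAEs and MAAEs are planned. They allow case review but do not replace a summary that the protocol specifies.

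**Conclusion.** The conflict is real and unreconciled: within the protocol (10.2 and 13.1.3 against 10.2.1 and 10.4.1), within the SAP (10.2.2 against the four table lists), and between the two documents. The consequence is an omitted, undeclared safety summary and a set of tables whose label does not describe their contents. Three targets are promised, and two, two, two and one are tabulated.

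The effect is confined to descriptive safety reporting. No immunogenicity result, sample size or error rate changes, and neither relatedness to trial vaccine nor the between-arm comparison is touched. The share of procedure-related events that are really routine-vaccine events cannot be derived from the documents.

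The conclusion assumes that the 10.4.1 list reflects the eCRF. If the eCRF already has a coded routine-vaccine field, only the SAP tables and the protocol wording remain to be corrected. The point should be acted on, because a protocol-specified summary is missing and the correction is cheap.

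**What to change.** 1. Derive a routine-vaccine relatedness flag from the assessment required by Protocol 10.2 and the suspected-procedure detail in 10.4.1.
2. In SAP 10.2.4.1, 10.2.5.1 and 10.2.6.1, split each trial-procedure table into routine vaccine and other trial procedure.
3. Add relationship to routine vaccine to SAP 10.2.7.1.
4. Reconcile Protocol 10.2.1 and 10.4.1 with 10.2 and 13.1.3, and word the Related and Not Related definitions for routine vaccine as well.
5. If the sponsor prefers not to report the summary, declare and justify the omission in SAP section 13.

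The cost is wording in both documents, one derived flag and the extra table splits. No new assessment of subjects is needed. If the suspected procedure is recorded as free text, someone must classify it by hand, which is best done while blinded and under a written rule.
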